3. STUDY OBJECTIVES

The specific aim of this study is to compare High-Dose NIATx Coaching/ECHO, Low-Dose NIATx Coaching/ECHO, High-Dose NIATx Coaching/No ECHO, and Low-Dose NIATx Coaching/No ECHO. Impact will be measured using the RE-AIM framework:

- *Reach* (primary aim) measured as the percent of eligible justice involved patients who 1) are initiated onto any MOUD (buprenorphine, extended-release injectable naltrexone, or methadone), and 2) engaged with MOUD use.
- *Effectiveness* measured in terms of impact of MOUD involvement on re-arrest rates.
- *Adoption* measured as the percent of eligible clinicians in jail and/or community providers who use MOUD.
- *Implementation* measured by an organizational readiness for MOUD implementation over time and intervention fidelity scale (*for NIATx and ECHO*).
- *Maintenance* measured as the likelihood of organizations sustaining provision of MOUD utilization (organizational sustainability scores at 12 and 24 months of intervention) and we will continue to collect Reach, Effectiveness, and Implementation measures during the maintenance phase (Ms 12-24).

Study Coordination

The UW-Madison Center for Health Enhancement Systems Studies (CHESS) and George Mason University Center for Advancing Correctional Excellence! are the coordinating sites for this study. George Mason holds the grant award for the larger study this research is embedded in. The UW site will oversee all recruitment and study implementation activities which includes:

- developing organizational site-specific recruitment and data collection processes that meet study objectives;
- training staff on protocol procedures prior to start of recruitment and continuous monitoring to assure compliance with the protocol and human subjects regulation;

- communicating with clinic site staff as needed via conference calls to monitor progress, inform of protocol changes/distribute new version of protocol, and address unanticipated issues or challenges;
- manage all study data;
- oversee analysis; and
- oversee publications and presentations.

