6. STUDY & TREATMENT PLAN

Study Design

The proposed study will implement a cluster randomized block design where staff are nested within sites. The community-based provider sites and jails will be grouped into homogeneous blocks and then randomly assigned into 2x2 design for each block. The forty-eights sites will be assigned to one of four study arms using a matching strategy within the blocks that groups four jail-clinic combination together prior to randomization. Each jail and CB treatment provider (or clinic) in these combinations will be treated as a site. For instance, if a jail has two post incarceration CB treatment providers (or clinics) in the trial, this will be 3 total sites (of the 48 sites). Within the matching block of 4 jail-clinic combinations, one jail-clinic combination will be randomized to an arm of the study. Twelve sites (that will consist of jails or post incarceration

CB treatment sites) will be assigned to each arm. The number of jails and post-incarceration sites per arm are expected to be balanced, with an anticipated 4 jails and 8 post-incarceration CB provider sites per arm.

Matching will be based on; a) number of clinic sites the jail will be including in the study (as part of the jail-clinic combination), population of the county where the jail is located, and whether or not the jail is currently providing MOUD to CJ population, and if so, what type of MOUD. The blocking procedure will reduce variability within treatment conditions and yield more precise estimates of treatment effects. This strategy will allow for the study team to examine the effects of High versus Low-Dose coaching and ECHO on MOUD use rates in large and small settings. In the study design, there will be a 12-month implementation period followed by 12 months to track sustainability. Data will be collected at baseline, 12 months and 24 months.

[figure not shown]
Intervention

There will be two “scaling-up practices” used in this study; NIATx Coaching and ECHO Clinical Mentoring. The study will look at combination of these two practices to create four intervention study arms;

- 1) High-Dose Coaching/ECHO,
- 2) Low-Dose Coaching/ECHO,
- 3) High-Dose Coaching/No ECHO, and
- 4) Low-Dose Coaching/No ECHO

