individuals who received naltrexone, buprenorphine and methadone and number of injections/slots. Captured data for the community-based treatment providers will include number referred from the jail for OUD, number receiving MOUD, number of individuals who received naltrexone, buprenorphine and methadone and number of injections/slots.

All suggested data requirements are included in the Information Sheet provided to each site prior to participation in the study.

Table 2: Measures, Sources, and Tool/Frequency

Measurement	Measure Source	Data Source/Frequency
Descriptive Statistics		

Organizational traits (survey source): Admissions (state), Rural v. Urban (state), organizational readiness (staff), MOUD type (org), funding (org), # of practitioners (org)
 
Client traits: Age, gender, ethnicity, highest education level, employment indicator, place of residence, type of offense, Medications/Treatment offered (date(s) receiving MOUD), mental health comorbidity, OUD history, Disciplinary actions/incident reports, types of offenses
 
Staff Characteristics: Age, Gender, Ethnicity, Certification or education level, years of training, tenure on the job
	Organization & Administrative Data	
 Organizational Survey 
 Baseline, 12m, 24m State CJ Database & Jail Administrative Database 
 Baseline, 12m, 24m Monthly Tracking Site Spreadsheet Organizational Survey 
 Baseline, 12m, 24m
Reach		
% of patients initiated/begin MOUD; Days engaged in MOUD	Organization	
 Monthly Tracking Site Spreadsheet 
 Completed by Jail/Clinic Manager/Data Liaison Or State Databases
Effectiveness		
Re-Arrest Data: Arrest dates, Arrest Offense (charge), Felony/Misdemeanor indication, Outcome (convicted, not convicted, sentence, start and end date of sentence),	State Database	
 State CJ databases 
 Baseline, 12m, 24m

Adoption		
% of prescribers using MOUD	Organization	
 • Organizational Survey 
 ○ Baseline, 12m, 24m
Staff Attitudes Toward MAT	Knudsen, Ducharme, Roman & Link ⁴²	
 • Staff Survey 
 ○ Baseline, 12m, 24m

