8. MEASUREMENT OF EFFECT

All scales used in this study, except for the Fidelity scales developed for this study, have good tested psychometric properties with similar populations. Listed below are the factors to be measured and measurement instruments with references to validation studies.

Descriptive Statistics - Organizational traits such as admission and rural v. urban will be obtained via Organizational Survey and database. Client traits such as age, gender, ethnicity, treatment offered and CJ status will also be obtained at three points during the study via the Organizational Survey and database. Staff traits such as gender, ethnicity, and certification or education level will be obtained via the Organizational Survey at three points.

REACH - The percent of patients initiated on MOUD and length of engagement will be obtained through monthly spreadsheet data completed by organizational staff or state databases.

Adoption – The percent of prescribers using MOUD will be collected through the Organizational survey at 3 points during the study. The organizations readiness for MOUD will be collected using the Organizational Readiness for Implementing Change (ORIC) scale and the Organizational Climate: Stress measure will be collected at two points in the study.

Effectiveness – Re-arrest rates will be obtained through state police databases on a yearly basis.

Maintenance –The organizational survey, which will be administered at three points during the study, will assess the likelihood of MOUD sustainability. The Physician Survey will be completed by physicians at 3 points during the study.

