We will test the mediation effect of each potential mediator at each time point as well as across time. The R package 'mediation,' will estimate the causal mediation effects, examine moderated mediation effects, and conduct sensitivity analysis.⁷⁰

Effectiveness analysis:

We will compare MOUD use and retention rates in the 4 different arms using hierarchical linear models, where arm membership is used as the treatment assignment. We will examine the distribution of this outcome measure and will implement an appropriate transformation or nonlinear link function when appropriate (e.g., logistic, Poisson, exponential). Monthly data collection of the Effectiveness as well as Reach (MOUD use) measures, allows for analysis after each stage of NIATx and ECHO.

Table 4: Initiation & Retention

	Data	Source
Initiation	
• # of clients initiated on MOUD• # on MOUD	Organizational Spread Sheet
Retention	
• # of injections• # of weeks on Buprenorphine (30-Day Discontinuation)• # of methadone doses	State Database

Qualitative Analysis:

The qualitative analysis will be conducted by project staff, supervised by the qualitative methodologist, who will ensure that proper and consistent interviewing and analysis techniques are used. Project staff will conduct the interviews, which will be audio recorded and transcribed verbatim. Interviews with leadership personnel will focus on organizational culture, including the organization's approach to making process changes, as well as motivations and expectations for working with justice-involved populations. Interviews with staff will focus on the staff's perspectives on their organizations' experiences with identifying and implementing process changes. Project staff will conduct a directed content analysis of these data. Qualitative data will be summarized and analyzed to detect patterns in individual and clinical approaches to change that have been successful. This description will enhance our understanding of how the NIATx and ECHO models work in criminal justice settings and criminally involved populations, promoting valuable insights that can be applied to future dissemination and implementation of evidence-based practices.

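### Engagement is defined per eligible patient in Section 3, but Section 10 analyses it as retention with no denominator; computed per starter, the arm comparison can reverse sign

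*Combined protocol and SAP*

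**What the plan says.** Section 3 names Reach as the primary aim and measures it as the "percent of eligible justice involved patients who 1) are initiated onto any MOUD". Engagement with MOUD is item 2 under the same stem, so it too is a percentage of eligible patients.

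The later sections describe engagement differently:

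- Section 6, Table 2, lists the percentage "of patients initiated/begin MOUD; Days engaged in MOUD". The second item is a duration, with no denominator.
- Section 8: "The percent of patients initiated on MOUD and length of engagement will be obtained through monthly spreadsheet data", or through state databases.
- Section 10, Effectiveness analysis: "We will compare MOUD use and retention rates in the 4 different arms using hierarchical linear models". Table 4 lists retention as the number of injections, the number "of weeks on Buprenorphine (30-Day Discontinuation") and the number "of methadone doses". Retention comes from the state database and initiation from the site spreadsheet.
- Section 10, Intervention and Sustainability, justifies mixed models by the clustering of patients on MOUD within programs. It gives frequency of use a separate model from the percentage using MOUD.

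No section gives the denominator of a retention rate, the value for an eligible patient who never starts, or the handling of a site or period with no starters.

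**The concern.** Weeks on buprenorphine and days engaged exist for a patient only after a start. Starting is the other half of the primary aim, and Section 6 describes coaching as a means to raise MOUD use. Whether a patient is a starter is therefore a post-randomisation event that the interventions are designed to change. If High-Dose coaching or ECHO brings in patients who would not have started otherwise, starters in different arms are different kinds of patients. Randomisation does not protect a comparison between them.

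Fixing a follow-up window or choosing a single retention metric would not remove this, because the problem lies in who is counted. What is at stake is the direction of the conclusion on half of the primary aim. An open denominator could also be settled after the results are known.

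**Working it through.** **The plan's own figure.** The documents give no retention figure. The nearest is the Section 10 power statement: 42 programs, 75 patients per program, ICC 0.10, d = 0.51, Type I error 0.05 (two-sided assumed), power .85 or higher.

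λ = d / √(4 × (ICC + (1 − ICC)/n) / J) = 0.51 / √(4 × (0.10 + 0.90/75) / 42) = 4.94

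With 40 degrees of freedom the power is 0.998, which meets the stated floor. The plan does not say whether the 75 are eligible patients or starters. If they are eligible and 20% start (15 per program), λ = 4.13 and power is 0.98. Precision is not the issue here; direction is.

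**Arm comparison under the two denominators.** All inputs in this step are assumed, because the documents give no start or retention rates. Let s₀ and s₁ be the proportions of eligible patients who start under Low-Dose and High-Dose. Let r₀ be retention in patients who would start in either arm, unchanged by arm, and let rₐ be retention in the added starters.

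- Difference among starters (High − Low): (s₀r₀ + (s₁ − s₀)rₐ)/s₁ − r₀ = ((s₁ − s₀)/s₁) × (rₐ − r₀)
- Difference per eligible patient: (s₁ − s₀) × rₐ

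The first takes the sign of rₐ − r₀. The second cannot be negative when s₁ exceeds s₀. With s₀ = 0.20, s₁ = 0.40 and r₀ = 0.60:

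| rₐ | Starters, High vs Low | Difference | Per eligible, High vs Low | Difference |
|---|---|---|---|---|
| 0.30 | 45% vs 60% | −15 points | 18% vs 12% | +6 points |
| 0.40 | 50% vs 60% | −10 points | 20% vs 12% | +8 points |
| 0.50 | 55% vs 60% | −5 points | 22% vs 12% | +10 points |
| 0.60 | 60% vs 60% | 0 | 24% vs 12% | +12 points |
| 0.70 | 65% vs 60% | +5 points | 26% vs 12% | +14 points |

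For rₐ = 0.40: (0.20 × 0.60 + 0.20 × 0.40)/0.40 = 0.50, and 0.40 × 0.50 = 0.20 against 0.20 × 0.60 = 0.12.

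**The same check in weeks.** Keep start rates of 20% and 40%, and assume 20 weeks for patients who would start in either arm and 10 weeks for added starters.

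- Per starter: (0.20 × 20 + 0.20 × 10)/0.40 = 15 vs 20 weeks, a difference of −5.
- Per eligible patient: 0.40 × 15 = 6 vs 0.20 × 20 = 4 weeks, a difference of +2.
- With a true 4-week gain in those who would start in either arm: per starter (0.20 × 24 + 0.20 × 10)/0.40 = 17 vs 20, a difference of −3; per eligible patient 6.8 vs 4.0, a difference of +2.8.

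An intervention that harms nobody and helps some can still look worse per starter.

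**Sites with no starters.** A per-starter value at such a site is 0/0. Assume 75 eligible patients per site and a beta-binomial with ICC 0.10, so that a = 9p and b = 9(1 − p). Then P(no starter) = B(a, b + 75)/B(a, b):

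| Start rate p | P(no starter) |
|---|---|
| 2.5% | 60% |
| 5% | 35% |
| 10% | 12% |
| 20% | 1.4% |

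Any loss would fall mainly on the arms with fewer starts, and it matters mainly at start rates of about 10% or below.

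**The case against.** The strongest reply is that the plan nowhere declares a starters-only analysis. The only denominator it states for engagement is the right one, in Section 3. This stands: a reader might infer that the second primary measure has been set up as a non-randomised comparison, and the documents do not support that. They show a denominator that is not carried from the objective into the measures and models, together with wording that leans towards starters.

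A reader might also infer that a site starting nobody leaves the analysis. No section says so. Injections and methadone doses taken as site totals would be 0, not missing, and Section 10 allows a Poisson link that accommodates zeros. Matching on "whether or not the jail is currently providing MOUD to CJ population" shows that some jails may begin without MOUD. Section 4, however, requires sites to agree to introduce or continue at least one medication, so persistent zero-start sites are less likely. The concern is confined to per-starter means and rates at low start rates.

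The reversal also depends on added starters being retained less well. The documents neither give nor exclude this, and the table shows no reversal at equal retention.

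Finally, ECHO aims at the quality of MOUD practice, so retention among treated patients is a fair secondary question, and a per-eligible measure partly reflects initiation. Both points stand. They support reporting the conditional result with a clear label, but they do not make it the comparison that answers Section 3.

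**Conclusion.** The point holds in conditional form. Half of the primary aim is defined per eligible patient and then measured and modelled without that denominator or a value for non-starters. Read in the ordinary way, Section 10 leads to a comparison among starters, which conditions on an event the interventions aim to change.

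Under the assumed rates, the estimate moves from 8 points in favour of High-Dose to 10 points against it. Across added-starter retention of 30% to 50%, the starters' comparison runs from 15 to 5 points against, while the per-eligible comparison runs from 6 to 10 points in favour. At 60% or above there is no reversal. These sizes rest on assumed start and retention rates. The mechanism rests only on the plan's own aim of raising MOUD use. The denominator should be settled before outcome data are analysed.

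**What to change.** In Section 10, state that the between-arm engagement comparison is the number engaged at a chosen time, or days engaged over a fixed window, per eligible patient as in Section 3. Count non-starters as not engaged (0 days), and keep sites and periods with eligible patients but no starters in the model at 0. Define eligible from the collected counts, for example screened positive in jails and referred from jail in community sites. Align Table 2, Section 8 and Table 4 with that definition. Report retention among starters as a secondary analysis, labelled as conditional on starting and not as a randomised effect.

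The cost is small but goes beyond wording. The monthly jail tracking in Section 6 lists the number screened, so a screen-positive (eligible) count must be added; the yearly jail administrative data, which are expected to include screening records, may supply it for past months. Numerators from the state database and denominators from the spreadsheet must be aligned by site. An eligible count is needed in any case, because Section 6 ranks sites for the 12-month interviews on the percentage of eligible people who received MOUD.

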11. RECORDS TO BE KEPT

- Organizational traits
- Staff/client traits
- Survey results (Organizational, staff and physician surveys)

12. ACRONYM LIST

BJA	Bureau of Justice Assistance
CFIR	Consolidated Framework for Implementation Research
CJ	Criminal Justice
CHESS	Center for Health Enhancement System Studies
CSAT	Center for Substance Abuse Treatment
D/I	Dissemination and Implementation
EBPs	Evidence-Based Programs
ECHO	Extension for Community Healthcare Outcomes
MAT	Medication Assisted Treatment
MOUD	Medications for Opioid Use Disorder
NIATx	Network for the Improvement of Addiction Treatment
OCM	Organizational Change Manager
OUD	Opioid Use Disorder
PDSA	Plan-Do-Study-Act
RCT	Randomized Control Trials
RE-AIM	Reach, Effectiveness, Adoption, Implementation, Maintenance
SAMHSA	Substance Abuse and Mental Health Services Administration
SUD	Substance Use Disorder
TAU	Treatment as Usual

